### Part A: Multiple Ascending Dose Cohorts (Cohorts 1-4)

Part A will consist of up to 4 cohorts of 9 subjects. Subjects will be randomly assigned to receive an oral dose of active IMP (6 subjects) or matching placebo (3 subjects) for 10 days in a sequential escalating manner with a minimum of 7 days interval between two cohorts.

In Part A, each cohort will follow a sentinel dose-escalation schedule; two (2) subjects will be dosed on the first dosing day of each cohort (1 subject on active IMP and 1 subject on matching placebo). The remainder of the cohort (5 subjects on active IMP and 2 subjects on matching placebo) will be dosed a minimum of 48 hours later pending confirmation of an acceptable safety profile in the dose-leader cohort by the Principal Investigator (PI), or medically-qualified designees who are familiar with the study protocol and Investigator's Brochure (IB).

The planned starting dose for Cohort 1 is 400 mg of DNDI-0690 once a day for 10 days. Doses to be administered in Cohorts 2 to 4 will be determined based on emerging PK and safety data. The number of daily doses may be increased to 2 by implementation of a twice a day (BID) dosing regimen if the number of capsules in a single intake is raising concerns of acceptability. This decision will be made by the Safety Review Committee (SRC) prior to each cohort and will apply to all subjects within a cohort.

Dose escalation between cohorts in Part A (and between Part A and Part B) will be temporarily stopped pending evaluation of all available data if any of the following criteria are fulfilled:

• A serious adverse reaction (*i.e.* a serious adverse event (SAE) considered at least possibly related to the IMP administration) occurs in one subject.

Or

• Severe non-serious adverse reactions (*i.e.* severe non-serious AE considered as, at least possibly related to the IMP administration) occur in two subjects in the same cohort, independent of within or not within the same system organ class.

Or

- If two or more subjects in the preceding dose group experience any of the following:
  - Alanine aminotransferase (ALT) or aspartate aminotransferase (AST) >3x upper limit of normal (ULN), considered clinically significant and IMP related.
  - Serum Cystatin C (Cys C) increase > 25%, confirmed after repeat assessment 24-48h apart, and considered IMP related.
  - o Ratio of microalbuminuria/creatininuria >300 mg/g and considered IMP related.

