  - An increase in corrected QT interval by Fridericia's formula (QTcF) value of >60 msec from baseline (average of baseline triplicate values) or an absolute QTcF >500 msec, both confirmed by repeat measurement after 20 minutes in resting position, and considered IMP related.

Or

- If one or more subjects in the preceding dose group experience:
  - o An increase in troponin I concentration which is considered clinically significant by the Investigator (with reference to the change from baseline value) and considered IMP related.

Or

• If the dose in a single subject is anticipated to exceed an AUC from time of dosing to the end of the dosing interval (AUC0-tau) of  $\geq$ 100 µg\*h/mL. These limits are based on the exposure observed at the 20 mg/kg in cynomolgus monkeys (no observed adverse effect level (NOAEL): AUC0-24 of 101 µg\*h/mL in male and 111 µg\*h/mL in females).

DNDi RD 777/34920 DNDi- 0690- 02

Final V3.0/ Date 07 December 2020

Confidential

Page 9 of 109

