#### IMP ADMINISTRATION

**DNDi** 

RD 777/34920

DNDi- 0690- 02

Capsules of DNDI-0690 100mg and 200 mg have been chosen as the formulation for this study. The number of capsules to be administered will vary depending on the dose selected by the SRC upon review of data (safety and PK) from the previous cohort.

Table 1 Description of DNDI-0690 doses

Part A	Dose		Incurace from the provious dass
rart A	mg	mg/kg/day*	Increase from the previous dose
Cohort 1	400 OD	5.7	
Cohort 2	To be decided	To be decided	2 to 3 times and/or change from OD to BID
Cohort 3	To be decided	To be decided	2 to 3 times and/or change from OD to BID
Cohort 4	To be decided	To be decided	2 to 3 times and/or change from OD to BID
Part B	maximum of 3600	maximum of 51.5	
Part C	To be decided	To be decided	Highest dose tested in Part A and well tolerated, or below

\* assuming a 70-kg person

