#### 10.2.2.3 Dose Escalation Stopping Criteria

Dose escalation between cohorts in Part A (and between Part A and Part B) will be temporarily stopped pending evaluation of all available data if any of the following criteria are fulfilled:

• A serious adverse reaction (*i.e.* a SAE considered at least possibly related to the IMP administration) occurs in one subject.

Or

• Severe non-serious adverse reactions (*i.e.*, severe non-serious AE considered as, at least possibly related to the IMP administration) occur in two subjects in the same cohort, independent of within or not within the same system organ class.

Or

• If two or more subjects in the preceding dose group experience any of the following:

DNDi RD 777/34920 DNDi- 0690- 02

Final V3.0/ Date 07 December 2020

Confidential

Page 50 of 109

- o ALT or AST >3xULN, considered clinically significant and IMP related.
- Serum Cys C increase > 25%, confirmed after repeat assessment 24-48h apart, and considered IMP related.
- o Ratio of microalbuminuria/creatininuria >300 mg/g and considered IMP related.
- o an increase in QTcF value of >60 msec from baseline (average of baseline triplicate values) or an absolute QTcF >500 msec, both confirmed by repeat measurement after 20 minutes in resting position, and considered IMP related.

Or

- If one or more subjects in the preceding dose group experience:
  - o an increase in troponin I concentration which is considered clinically significant by the Investigator (with reference to the change from baseline value) and considered IMP related.

Or

• If the dose in a single subject is anticipated to exceed an AUC0-tau of  $\geq 100 \, \mu g^*h/mL$ . These limits are based on the exposure observed at the 20 mg/kg in cynomolgus monkeys (NOAEL: AUC0-24 of 101  $\mu g^*h/mL$  in male and 111  $\mu g^*h/mL$  in females).

Or

• If the dose in a single subject is anticipated to exceed a  $C_{max}$  of  $\geq 8.0 \ \mu g/mL$ . These limits are based on the exposure observed at the 20 mg/kg in cynomolgus monkeys (NOAEL:  $C_{max}$  of  $8.03 \ \mu g/mL$  in males and  $9.03 \ \mu g/mL$  in females).

Dose escalation between cohorts in Part A will be limited to a maximal 3-fold increase, and 2-fold increase between Part A and Part B, depending on safety and tolerability data and predicted exposure (both AUC and  $C_{max}$ ).

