Steady state is expected to be reached within 3 days maximum based on the observed geometric mean  $t_{1/2}$  (ranging from 4.547 to 12.144 hours, depending on doses). Based on the minimally acceptable duration of VL treatment of 14 days as per the VL Combination therapy Target Product Profile, the duration of the present repeated dosing study was chosen to be 10 days. As steady state will likely be reached in 3 to 4 days, a duration of 10 days seems sufficient to describe the safety profile of DNDI-0690 in healthy volunteers.

Reversible and non-clinically relevant elevations of the creatinine levels were identified in healthy volunteers during the SAD. This pattern of slight increase in creatinine may be explained by an inhibition of creatinine secretion by cellular transporters. DNDI-0690 was assessed *in vitro* against a panel of drug transporters, showing 27.4 and 55.1 % inhibition of multidrug and toxin extrusion1 (MATE1; expressed in human embryonic kidney (HEK) cell line) at concentrations of 1 and 10  $\mu$ M DNDI-0690, respectively. This effect could explain the

DNDi RD 777/34920 DNDi- 0690- 02

Final V3.0/ Date 07 December 2020

Confidential

Page 52 of 109

moderate increase in plasma creatinine which was observed in the SAD study. Of notice, MATE2 was unaffected in the *in vitro* studies.

Proper follow-up of renal function in the MAD, including the monitoring of plasma creatinine, BUN and biomarkers not affected by enzymatic transporters such as Cys C, will be ensured. A specific exploration of the renal function is proposed in part C of the MAD study with administration of iohexol, a non-ionic contrast agent used as marker freely filtrated by the glomerulus, and measure of its plasma clearance in order to establish the GFR in placebo and DNDI-0690 treated healthy subjects.

Dose escalation between cohorts will be limited to a 2-3-fold increase depending on safety and tolerability data and predicted exposure (both AUC and  $C_{max}$ ).

The highest scheduled dose in Part A is set to 2400 mg/day. In addition, if safety stopping criteria are not met, a higher dose may be considered (up to a maximum of 3600 mg/day) for assessment of QT, but likely based on a shorter duration of treatment (see below Part B).

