#### 10.3.2 Part B

Safety pharmacology studies have shown that DNDI-0690 had no effects on CNS, respiratory function, and cardiovascular system. The absence of any effect on cardiovascular system was confirmed in vivo in the telemetry study in conscious cynomolgus monkeys, where no effects on cardiovascular parameters and body temperature were seen up to the single dose of 350 mg/kg.

There were no clinically significant findings in ECG results and no notable increases in QTcF interval in the SAD healthy volunteer study up to 3600 mg.

However, some heart changes as a consequence of nephrotoxicity were considered agonal in their nature and contributory to death together with renal changes in animal studies.

- Therefore, circulating levels of troponin I will continue to be monitored in the MAD study in healthy subjects at admission, at last day of treatment and in case of any ECG clinically significant abnormality during the course of treatment.
- In addition to safety ECGs, the effect of DNDI-0690 on Holter ECG parameters will be assessed in Part A and Part B.

Part B will only be implemented if the cardiac pharmacodynamic assessment (supratherapeutic dose) is needed and if the SRC considers safe to proceed to a daily dosing above 2400 mg (with a maximum allowed dose of 3600 mg).

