  - Ae%: % of dose excreted in urine over each collection interval (0 to 24 h post-dose).
  - CLR: Renal clearance

If BID dosing, AUC0-10, AUC0-10/D, AUC0-10h,norm will be added on Day 1 and Day10.

Derived PK parameters will be listed along with the points used to calculate  $k_{el}$  (lower, upper and number used) and  $R^2$  adjusted. The derived PK parameters will also be summarised. The descriptive statistics presented will be N, n, arithmetic mean, geometric mean (with the exception of  $T_{max}$ ), SD, coefficient of variation (CV%), minimum, median and maximum.

**Dose Proportionality/Independence (Part A and Part B):** For Day 1 and Day 10 (Part A) OR Day 1 and Day 5 (Part B), dose proportionality will be assessed by performing a regression analysis of the log-transformed  $C_{max}$ ,  $AUC_{0-\tau}$  and  $AUC_{0-inf}$  (Day 10 for Part A and Day 5 for Part B only) values versus the log-transformed dose using the power model with a fixed effect for log(dose). For each parameter a point estimate and 95 % confidence interval (CI) will be calculated for the slope of the regression line.

For Day 10 for Part A and Day 5 for Part B, dose independence will be assessed for t½ and CL/F by performing a regression analysis of the untransformed parameters versus dose with a fixed effect for dose. For each parameter a point estimate and corresponding 95 % CI will be calculated for the slope of the regression line.

**Steady-State** (**Part A and Part B**): For each dose level, log-transformed trough concentration levels at pre-dose each day (Day 2 to Day 10 for Part A and Day 2 to Day 5 for Part B) will be subjected to a mixed effects analysis of variance (ANOVA) with study day as a fixed effect and subject as a random effect in order to establish whether and when steady-state has been attained for each dose level. Back-transformed ratios for the comparisons of each consecutive day (*i.e.* Day 3/Day 2) will be presented along with corresponding 90 % CI.

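### If BID dosing is used, the AUC stopping limit applies a 24-hour NOAEL exposure to a single dosing interval; the fold ceilings also need a stated daily-dose basis

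*Protocol*

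**What the plan says.** **Exposure limit.** The synopsis (Part A) halts escalation if the dose in a single subject "is anticipated to exceed an AUC from time of dosing to the end of the dosing interval" of 100 µg·h/mL or more. Section 10.2.2.3 repeats this as AUC0-tau. Both give the source as the monkey NOAEL at 20 mg/kg, with AUC0-24 of 101 (males) and 111 (females) µg·h/mL. Table 3 shows that this NOAEL dose was given as 10 mg/kg twice daily. Section 8.7 states the same stopping criterion as AUC0-24 of 100,000 ng·h/mL or more.

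**BID option.** The safety review committee may switch a Part A cohort to BID "if the number of capsules in a single intake is raising concerns of acceptability". The second dose follows the first by 10 h (10.5.3.1), so the intervals are 10 h and 14 h. For BID, 10.9.2.5.4 says that AUC0-10 and its normalised forms "will be added on Day 1 and Day10". On Day 10 only the morning dose is given. Section 10.2.1 bases escalation on PK to 24 h after the last dose, with Cmax and AUC0-24 as the minimum.

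**Step size.** Section 10.2.2.3 and the synopsis say "Dose escalation between cohorts in Part A will be limited to a maximal 3-fold increase, and 2-fold increase between Part A and Part B"; 10.3.1 says "Dose escalation between cohorts will be limited to a 2-3-fold increase depending on safety and tolerability data and predicted exposure". Table 1 describes each step for Cohorts 2 to 4 as "2 to 3 times and/or change from OD to BID". Elsewhere the limits are daily: "The highest scheduled dose in Part A is set to 2400 mg/day" (10.3.1), and Part B goes ahead only "if the SRC considers safe to proceed to a daily dosing above 2400 mg" (10.3.2).

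**The concern.** A limit on AUC must be measured over the same time span as the exposure it came from. Here the number is a 24-hour figure and the variable is a dosing-interval figure. The mismatch is invisible under OD and appears as soon as a cohort goes BID, because each interval then carries only part of the day's exposure. The kidney is the main target organ and monkeys died at doses above the NOAEL (8.5.1), so the limit matters.

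The observed data available at the review do not correct it. A Day 10 AUC0-24 under BID contains one dose instead of two and understates the daily exposure of the cohort just completed.

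The fold ceilings raise a smaller issue of the same kind. A change from OD to BID makes dose per intake and dose per day diverge by a factor of two, and the rule does not say which it limits.

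**Working it through.** **The plan's own figures.** Table 1 gives 400 mg OD as 5.7 mg/kg/day; 400/70 = 5.71, so that column is a daily figure. With tau = 24 h, AUC0-tau and AUC0-24 are the same quantity, so the limit is sound under OD.

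**Inputs (Table 4, 1200 mg, single dose, ng·h/mL).** AUC0-12 13,400; AUC0-24 19,700; AUC0-inf 25,100. The case worked is 1200 mg BID, the largest BID regimen within 2400 mg/day. Linear superposition is assumed, as in 10.3.1.

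1. *Daily exposure.* Steady-state AUC over 24 h = 2 × 25,100 = 50,200. (Doubling Table 4's predicted OD value gives 2 × 23,600 = 47,200.)
2. *Terminal rate.* AUC still to come is 25,100 − 13,400 = 11,700 at 12 h and 25,100 − 19,700 = 5,400 at 24 h. k = ln(11,700/5,400)/12 = 0.0644 per h. Over 24 h the curve falls to 5,400/11,700 squared = 0.213.
3. *AUC to come at other times.* 10 h: 11,700·e^(2k) = 13,309. 14 h: 11,700·e^(−2k) = 10,285. 34 h: 5,400·e^(−10k) = 2,835.
4. *Steady-state AUC in the 10 h interval.*
   - Same day's morning dose: 25,100 − 13,309 = 11,791.
   - Earlier morning doses: (5,400 − 2,835)/(1 − 0.213) = 3,259.
   - Earlier evening doses: (10,285 − 5,400)/(1 − 0.213) = about 6,208.
   - Sum: about 21,260.
5. *Share of the day.* 10 h interval: 21,260/50,200 = 42%. 14 h interval: 28,940/50,200 = 58%.
6. *Looseness.* 1/0.423 = 2.4 and 1/0.577 = 1.7. A 100,000 limit per interval is reached only at a 24 h AUC of about 236,000 (10 h) or 173,000 (14 h).
7. *Day 10, morning dose only.* The missing evening dose would have added its first 14 h: 25,100 − 10,285 = about 14,800. Day 10 AUC0-24 = 50,200 − 14,800 = 35,400, which is 29.5% low (14,800/47,200 = 31% from the other starting value).

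**Chance of passing 100,000 at 1200 mg BID.** Exposure is taken as lognormal, with Table 4 CVs read as geometric and sigma = √ln(1 + CV²).

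| Basis | Central value | CV 23.5% | CV 48.9% | CV 63.9% |
|---|---|---|---|---|
| 24 h | 50,200 | 0.15% | 6.8% | 11.9% |
| 14 h interval | 28,940 | <0.01% | 0.4% | 1.7% |
| 10 h interval | 21,260 | <0.01% | 0.04% | 0.4% |

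The CVs are those of 3600 mg at steady state, 1200 mg single-dose AUC0-24 and 1200 mg AUC0-inf.

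**Fold ceilings.** 400 mg OD to 1200 mg BID is 1200/400 = 3-fold per intake and 2400/400 = 6-fold per day. From 1200 mg BID in Part A to 3600 mg OD in Part B is 3600/2400 = 1.5-fold per day (allowed) but 3600/1200 = 3-fold per intake (over the 2-fold ceiling). The two readings then give opposite answers.

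**The case against.** *The intent is 24 h anyway.* Section 8.7 says AUC0-24, the source is a 24 h AUC, and 10.2.1 requires AUC0-24 at every review. This shows what was meant, but the rule that operates is the one in 10.2.2.3 and the synopsis, and those say AUC0-tau. The 8.7 sentence is also about Cohort 1, which is OD, where the terms coincide. The AUC0-24 required by 10.2.1 is the Day 10 value, which under BID lacks the evening dose.

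*The criterion is a prediction.* It concerns anticipated exposure, so an incomplete Day 10 profile does not change the limit itself. That is right, but the prediction for the next cohort rests on these data.

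*The larger factor uses only the shorter interval.* Fair; the range 1.7 to 2.4 is the correct statement.

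*Other safeguards remain.* BID is optional. Sentinel dosing, the Cmax limit, the 2400 mg/day maximum and joint review all apply. Mean daily AUC at 1200 mg BID is about half the limit, and Cmax is at most 2 × 1,990 = 3,980 ng/mL on average, half of 8,000. This all stands.

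*A stronger reading of the fold ceilings.* A reader might infer from Table 1 that the plan authorises a jump from 400 mg OD to 1200 mg BID. The documents do not support that. The absolute maxima are per day, Table 1 has a mg/kg/day column, and its and/or wording also fits raising the daily dose, splitting it, or both. BID is a remedy for capsule burden, yet 1200 mg is six 200 mg capsules and the single-dose study gave 18 at once.

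**Conclusion.** The AUC limit is mis-specified for BID dosing and correct for OD. As written it is about 1.7 times (14 h interval) to 2.4 times (10 h interval) looser than the 24 h NOAEL exposure it is taken from. The Day 10 AUC0-24 seen at review is about 30% below true daily exposure under BID. The fold ceilings are an ambiguity and not an error: the likely meaning is total daily dose, and a 6-fold daily step is a possible but unlikely reading.

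The sizes rest on linear superposition, a single terminal rate from 10 h onward, and Table 4 data from fasted males at 1200 mg. The share of subjects above 100,000 over 24 h runs from 0.15% to about 12% depending on the CV chosen, so it is illustrative only. A reader might infer that subjects would be dosed past the NOAEL exposure; the documents do not show that, since mean predicted exposure stays near half the limit and no unsafe step follows. The case for change is that a stated safety limit in healthy volunteers should be on the same time base as its source.

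**What to change.** 1. In the synopsis (Part A) and 10.2.2.3, replace AUC0-tau in the exposure limit with predicted steady-state AUC over 24 h, counting both doses if BID. This also brings them into line with 8.7.
2. In 10.2.1, state that under BID the Day 10 morning-only AUC0-24 is not to be used as daily exposure. Daily exposure can be predicted by superposition, the method already used in 10.3.1.
3. As a secondary clarification, state in the synopsis, 10.2.2.3 and 10.3.1 that the 3-fold and 2-fold ceilings apply to total daily dose. Reword the three Table 1 cells to: *up to 3 times the previous total daily dose, given OD or BID*.

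The cost is a few phrases and three table cells, with no extra samples or subjects. The only downside is slightly less freedom when BID is introduced.

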## 10.3 Discussion of Study Design, including the Choice of Control Groups

#### 10.3.1 Part A

The starting dose for this multiple dose-escalation study was selected on the basis of the results of the SAD study in human healthy volunteers: at the highest administered dose (3600 mg), the AUC $_{0-inf}$  geometric mean was 47,800 (Geometric CV%: 26.7) ng.h/mL and the  $C_{max}$  geometric mean was 2560 (Geometric CV%: 20.7) ng/mL.

Final V3.0/ Date 07 December 2020

Confidential

Page 51 of 109

DNDi RD 777/34920 DNDi- 0690- 02

Predictions of steady state exposures have been performed simulating repeated doses at the actual dose levels administered in the SAD study in healthy male subjects in fasted condition. Actual single dose data at each dose level were used to predict its own steady state levels.

The performed non-parametric super positioning assumed linearity over time following repeated dosing. The following exposures were predicted for once a day dosing at steady state:

Table 4 Geometric Mean (CV%) Key Observed in the Single Ascending Dose Study and Predicted Pharmacokinetic Parameters of DNDI-0690 in Male Healthy Volunteers

DNDI- 0690			ed Parameters (CV%)		Predicted Parameters at Steady State after Once Daily Dosing (CV%)						
	Cmax (ng/mL)	AUC(0-12) (ng.h/mL)	AUC(0-24) (ng.h/mL)	AUC(0-inf) (ng.h/mL)	Cmax (ng/mL)	AUC(0-tau) (ng.h/mL)	Accumulation Ratio				
10 mg	172 (26.9%)	1140 (46.3%)	1470 (61.4%)	1640 (77.9%)	182 (39.4%)	1570 (77.7%)	1.07 (13.9%)				
30 mg	496 (29.1%)	3530 (40.1%)	4650 (50.1%)	5270 (62.0%)	534 (35.0%)	4980 (62.8%)	1.07 (11.5%)				
150 mg	775 (25.6%)	5380 (49.4%)	7060 (66.8%)	7720 (78.4%)	827 (31.6%)	7240 (76.8%)	1.03 (8.09%)				
400 mg	1120 (24.1%)	8500 (39.4%)	11800 (53.6%)	13900 (67.5%)	1240 (32.5%)	13100 (65.8%)	1.11 (10.6%)				
1200 mg	1670 (25.2%)	13400 (35.2%)	19700 (48.9%)	25100 (63.9%)	1990 (37.2%)	23600 (64.2%)	1.20 (14.3%)				
3600 mg	2600 (18.8%)	21200 (21.6%)	32800 (24.5%)	47100 (24.2%)	3380 (18.5%)	44900 (23.5%)	1.37 (6.63%)				

Exposure after multiple dose of 400 mg OD are predicted to reach a mean (CV%) exposure of  $C_{max}$  1240 (32.5%) ng/mL and an  $AUC_{0-\tau}$  13,100 (65.8%) ng.h/mL, which remains below the maximum exposure measured after single dose without safety concerns (see Table 4). The dose of 400 mg OD is thus considered a safe starting dose for multiple dosing.

Steady state is expected to be reached within 3 days maximum based on the observed geometric mean  $t_{1/2}$  (ranging from 4.547 to 12.144 hours, depending on doses). Based on the minimally acceptable duration of VL treatment of 14 days as per the VL Combination therapy Target Product Profile, the duration of the present repeated dosing study was chosen to be 10 days. As steady state will likely be reached in 3 to 4 days, a duration of 10 days seems sufficient to describe the safety profile of DNDI-0690 in healthy volunteers.

Reversible and non-clinically relevant elevations of the creatinine levels were identified in healthy volunteers during the SAD. This pattern of slight increase in creatinine may be explained by an inhibition of creatinine secretion by cellular transporters. DNDI-0690 was assessed *in vitro* against a panel of drug transporters, showing 27.4 and 55.1 % inhibition of multidrug and toxin extrusion1 (MATE1; expressed in human embryonic kidney (HEK) cell line) at concentrations of 1 and 10  $\mu$ M DNDI-0690, respectively. This effect could explain the

DNDi RD 777/34920 DNDi- 0690- 02

Final V3.0/ Date 07 December 2020

Confidential

Page 52 of 109

moderate increase in plasma creatinine which was observed in the SAD study. Of notice, MATE2 was unaffected in the *in vitro* studies.

Proper follow-up of renal function in the MAD, including the monitoring of plasma creatinine, BUN and biomarkers not affected by enzymatic transporters such as Cys C, will be ensured. A specific exploration of the renal function is proposed in part C of the MAD study with administration of iohexol, a non-ionic contrast agent used as marker freely filtrated by the glomerulus, and measure of its plasma clearance in order to establish the GFR in placebo and DNDI-0690 treated healthy subjects.

Dose escalation between cohorts will be limited to a 2-3-fold increase depending on safety and tolerability data and predicted exposure (both AUC and  $C_{max}$ ).

The highest scheduled dose in Part A is set to 2400 mg/day. In addition, if safety stopping criteria are not met, a higher dose may be considered (up to a maximum of 3600 mg/day) for assessment of QT, but likely based on a shorter duration of treatment (see below Part B).

The animal data suggest that >95% efficacy can be achieved in all independent models when an AUC $_{\text{cum,u}}$  of 4.0  $\mu$ g/mL\*h was reached. Based on prediction of exposure in the MAD, a daily dose of 400 mg DNDI-0690 administered for 10 days may provide a highly efficacious treatment regimen. However, due to the variability in exposure between subjects seen in the SAD, the required exposure may not be reached for all subjects, and a dose up to 2400 mg may be required to achieve plasma levels at which efficacy is expected.

